10.5.5 Pharmacokinetics

10.5.5.1 Trough concentrations

Pre-dose (Cmin) plasma concentrations of alpelisib and fulvestrant will be reported in summary statistics presenting n (number of values to be reported), arithmetic mean, geometric mean, median, standard deviation, coefficient of variation CV (%), Geometric mean CV (%), minimum and maximum using the PAS. Figures of geometric mean and arithmetic mean (+/- standard deviation) of alpelisib and fulvestrant trough concentrations over time will also be presented for the PAS.

The fulvestrant pre-dose plasma concentration will be compared between both arms with or without concomitant alpelisib administration. The time-course of pre-dose plasma concentrations to reach steady state will be assessed using a descriptive approach.

A [REDACTED] will be used to [REDACTED]

A [REDACTED] will be used to [REDACTED]

(such as selected [REDACTED])

[REDACTED]

[REDACTED]

[REDACTED]
[REDACTED]

[REDACTED]

10.5.5.2.1 Individual Bayesian estimates

The listing of empirical Bayes estimates of the individual PK parameters will be provided for the patients treated with alpelisib and included in the PAS of this study using a population PK model. The individual concentration vs. time profile at steady state will be simulated. For each of the concentration vs. time profile, the Cmax, AUCtau and t1/2,eff will be determined. Concentrations and appropriate individual PK parameters of alpelisib will be reported in summary statistics presenting n (number of values to be reported), m (number of non-zero

[REDACTED]

values to be reported) arithmetic mean, geometric mean, median, SD, coefficient of variation CV (%), Geometric mean CV (%), minimum and maximum.

Geometric mean and the geometric CV (%) will be derived from non-zero concentrations. Concentrations below the limit of quantitation will not be imputed and will be treated as zero in summary statistics.

Further [REDACTED] might be performed to investigate any

10.5.5.3 Data handling principles

Detailed data handling methods will be addressed in the statistical analysis plan.

A large black rectangular redaction box covers the majority of the page content, from approximately y=113 to y=886. The redaction is irregular, with some white space visible at the top and bottom edges. There are also several smaller black rectangular redaction boxes located at the top left, top right, and bottom left corners of the main redacted area.

A large black rectangular redaction box covers the majority of the page content, from approximately y=113 to y=886. The redaction is composed of several horizontal black bars of varying lengths, with a few small white rectangular gaps. The top and bottom edges of the redaction are aligned with the page's top and bottom margins.

For more information, contact the Office of the Vice President for Research and the Office of the Vice President for Student Affairs.

10.7 Interim analysis

10.7.1 Primary endpoint: Progression-free survival in the *PIK3CA* mutant cohort

Two interim analyses are planned after approximately 97 and 185 of the 243 targeted PFS events (40% and 76% information fractions respectively) have been documented. These analyses are expected to take place around 19 and 25 months from the date of first patient randomized in the study. Approximately 243 patients are expected to be randomized when the 97th PFS event occurs at the time of the first interim analysis if H_0 is true (HR.=1). The primary intent of the first interim analysis is to allow the cohort to stop early for lack of efficacy (futility). There is no intent to carry out an analysis to declare superior efficacy at the time of the first interim analysis. The second interim analysis will allow the study to stop early for outstanding efficacy. The second interim analysis will only be carried out after all patients have been randomized in the *PIK3CA* mutant cohort and approximately 76% of the 243 targeted PFS events have been observed.

The assessment of futility will be guided based on two criteria,

A user-defined gamma spending function ($\gamma=5$) will be used as a beta-spending function to determine the non-binding futility boundary. One important feature of the design is that the efficacy stopping boundaries will not be affected by the presence of non-binding futility stopping boundaries.

Based on the choice of α -spending and β -spending function described above, the futility boundary in terms of p-value scale (or Z-statistic scale) at the interim is calculated as $p=0.128$ (or $Z=1.134$). The observed (i.e. nominal) p-value has to be greater than 0.128 to conclude futility according to this criterion at the time of the first interim analysis.

In addition to the stopping boundary based on the β -spending function described above, DMC will be instructed to include in their recommendation whether the conditional probability of observing a clinically relevant PFS treatment effect at the final PFS analysis is less than 0.20, i.e.:

$$\text{Conditional probability } (\text{HR}_{\text{final}} \leq 0.6 | \text{HR}_{\text{interim}}) < 0.20$$

This criterion uses the observed interim data and an assumption regarding the distribution of future unobserved data at the final analysis, conditioned under the alternative hypothesis (HR.=0.6). The futility boundary for this criterion in terms of p-value scale at the interim is calculated as $p=0.068$. Thus the observed (i.e. nominal) p-value has to be greater than the p-value scale futility boundary = 0.068 to conclude futility according to this criterion.

Details of the methodology as well as the operating characteristics for the futility criterion based on conditional probability is described in [Appendix 6](#).

Therefore at the time of the futility analysis, the PIK3CA mutant cohort may be stopped for futility if one or both of the criteria are met.

In addition, the predictive probability of success based on the final planned number of PFS events will be calculated given the interim data, and provided to the DMC at the time of the futility interim analysis as supportive information.

A Haybittle-Peto stopping boundary (as implemented in East 6.3) will be used for interim and final PFS analyses. At the second interim analysis, the observed p-value has to be less than or equal to 0.0001 (or $Z=3.719$) in order to conclude superior efficacy. If the study continues to final analysis, the p-value that will be used to declare statistical significance at the final analysis will be 0.0199 ($Z=2.054$).

Since the observed number of events at the interim analyses may not be exactly equal to the planned number of events, the efficacy and futility boundaries will need to be re-calculated (or updated) based on the actual number of observed events using the pre-specified Haybittle-Peto boundary and β -spending function. Therefore, the observed p-values at the interim analyses will be compared with the updated boundaries.

If the study continues to final analysis, the p-value that will be used to declare statistical significance at the final analysis will be based on the actual number of PFS events documented at the cut-off date for the final analysis and the alpha already spent at the interim analysis. Therefore, if the interim analyses were carried out after exactly 40% and 76% of the planned number of events, and the cohort continued until the final analysis, the observed p-value will have to be less than 0.0199 to declare statistical significance. If the number of events in the final analysis deviates from the expected number, the final analysis criteria will be determined so that the significance level is maintained at 0.02 in this cohort.

Statistical properties of the group sequential design in this cohort are summarized in [Table 10-1](#) below.

Table 10-1 Simulated probabilities to stop for futility or efficacy at the interim or final analysis in the PIK3CA mutant cohort

Scenario	Look	# PFS events	Cumulative probabilities (%)		Incremental probabilities (%)	
			Stop for efficacy	Stop for futility	Stop for efficacy	Stop for futility
Under H_0 (HR=1)	Interim 1	97	0	92.98	0	92.98
	Interim 2	185	0.02	-	0.02	-
	Final	243	0.98	-	0.96	-
Under H_a (HR=0.6)	Interim 1	97	0.34	15.31	0.34	15.31
	Interim 2	185	38.50	-	38.50	-
	Final	243	83.95	-	45.45	-

Note: The study will not stop for outstanding efficacy at the first (futility) interim analysis. Operating characteristics performed in SAS v9.4 with 10,000 simulations and random seed = 111064

Interim PFS analysis in the PIK3CA mutant cohort will be performed by an independent statistician (not involved with the conduct of the study). Further details will be described in the DMC Charter. The results of the interim analyses will be provided to the DMC by the independent statistician.

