If the true hazard ratio is 0.6 (under alternative hypothesis), a total of 243 PFS events are required to have 83.80% power at an one-sided overall 2.0% level of significance to reject the null hypothesis (HR.=1) using a log-rank test for a 3-look group sequential design using a Haybittle-Peto boundary to determine the efficacy boundary along with (i) a gamma spending function ($\gamma = 5$) and (ii) a conditional probability function to determine the non-binding futility boundaries. Assuming that 40% of the patients will have a *PIK3CA* mutant status, an enrollment rate of 12 patients during the first 6 months (5 with *PIK3CA* mutant status), 35 patients up to 12 months (14 with *PIK3CA* mutant status) and 59 patients afterwards (24 with *PIK3CA* mutant status) and 10% patients will be lost to follow-up for PFS final analysis, a total of 340 patients will need to be randomized in this cohort to the two treatment arms in a 1:1 ratio. Given the above assumptions, it is estimated that the 243rd PFS event will be observed at approximately 32 months from the date of first patient randomized in the cohort.

The estimated timelines for interim and final PFS analyses are provided in [Table 10-4](#).

Table 10-4 Estimated timelines for interim and final PFS analyses in the *PIK3CA* mutant cohort

Look	Months after randomization of the first patient	Number of PFS events	Number of patients expected to be randomized (HR.=1).
Interim 1 (futility)	19	97	271
Interim 2 (efficacy)	25	185	340
Final	32	243	340

Patients with *PIK3CA* non-mutant status:

The proof of concept criteria require:

(a) an estimate for PFS HR reaching a critical value i.e. $HR \leq 0.60$

(b) strong evidence that the treatment results in a HR that is better than the value of no interest. i.e. Posterior Probability (HR < 1) $\geq 90\%$

Based on the dual criteria a minimum of 102 PFS events are required (please refer to [Section 14.6](#)). Assuming an enrollment rate of 12 patients during the first 6 months (7 with *PIK3CA* non-mutant status), 35 patients up to 12 months (21 with *PIK3CA* non-mutant status) and 59 patients afterwards (35 with *PIK3CA* non-mutant status) and 10% patients will be lost to follow-up, 220 patients will be randomized (110 per arm), in order to observe the required 102 PFS events in approximately 18 months (if the observed HR is 0.60 and the median PFS for the control arm is 7.4 months).

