14.6 Appendix 6 - Statistical methodology

14.6.1 Statistical methodology and operating characteristics – PFS futility criteria in the PIK3CA mutant cohort

At the time of the futility analysis, the cohort may be stopped for futility if one or both of the following criteria are met:

1. The observed (i.e. nominal) p-value > 0.128
2. Conditional Probability ($HR_{final} \leq 0.6 | HR_{interim}$) < 0.20

Criterion (2) uses the observed interim data and an assumption regarding the distribution of future unobserved data in the two treatment groups conditioned under the alternative hypothesis (HR_{Ha}). Under the alternative hypothesis, the following formula ([Jennison and Turnbull 2000 formula 10.2](#)) can be used to find the futility boundary on the Z-statistic scale (z_t) for criterion (2) that satisfies:

$$\Phi \left[-\frac{1}{\sqrt{1-t}} \left(z_{\alpha'} - \sqrt{t} z_t - \sqrt{1-t} \frac{-\log HR_{Ha}}{\sqrt{\left(\frac{a}{D(1-t)} \right)}} \right) \right] < 0.2$$

where:

$a = \frac{(r+1)^2}{r}$ with $r:1$ randomization ratio for treatment and control,

D : Total number of PFS events,

t : Information fraction at the futility interim analysis (i.e. 0.4)

$z_{\alpha'}$: Final boundary on Z scale,

z_t : Observed value on Z scale at futility interim

The critical value for the Z-statistic at the futility interim analysis that will ensure criterion (2) is satisfied is $|z_t| = 1.489$. The futility boundary in terms of p-value scale is thus calculated as $p = 0.068$.

The operating characteristics of the revised futility criteria are provided in [Table 14-11](#).

Table 14-11 Operating characteristics for PFS futility criteria in the PIK3CA mutant cohort

Futility Criteria	Probability to be stopped for futility	
	Under Criterion 1 only	Under Criterion 2
True HR		
1.0	86.95%	92.98%
0.6	8.89%	15.31%

Criterion 1: Observed (i.e. nominal) p-value greater than 0.128

Criterion 2: Conditional Probability ($HR_{final} \leq 0.6 | HR_{interim}$) < 0.20

Note: Operating characteristics for criterion 1 performed in East 6.3 with number of simulations = 10,000 and randomization seed = 37275. Operating characteristics for criterion 2 performed in SAS v9.4 with 10,000 simulations and random seed = 111064

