 - Planned final analysis of PFS when targeted number of PFS events is expected to be observed (first OS interim analysis, if not tested at s_2)

- Planned second interim analysis of OS.
- Planned final analysis of OS
- Let $t_{PFS(s1mut)}$, $t_{PFS(s2mut)}$, $t_{PFS(s3mut)}$ represent information fractions for PFS at time points $s1mut$, $s2mut$, $s3mut$, respectively.
- Let $t_{OS(s2mut)}$, $t_{OS(s3mut)}$, $t_{OS(s4mut)}$, $t_{OS(s5mut)}$ represent information fractions for OS at time points $s2mut$, $s3mut$, $s4mut$, $s5mut$, respectively.
- $u_{mut}(t_k)$ and $v_{mut}(t_k)$ are the efficacy stopping boundaries for PFS and OS, respectively, at information fraction t_k .
- $l_{mut}(t_{PFS(s1mut)})$ is the futility stopping boundaries for PFS at the first interim analysis

Using the following testing strategy, the overall type-I error rate can be controlled:

1. During the first PFS interim analysis, test PFS at $\alpha_{mut}(t_{PFS(s1mut)})$:
 - If the futility boundary for PFS, $l_{mut}(t_{PFS(s1mut)})$ is crossed then stop the study for futility, otherwise go to step 2.
 - Note there is no intent to test OS at the first PFS interim analysis.
2. During the second PFS interim analysis, test PFS at $\alpha=0.0001$:
 - If the PFS efficacy boundary $u_{mut}(t_{PFS(s2mut)})$ is crossed then test OS at $\delta_{mut}(t_{OS(s2mut)})$.
 - If the OS efficacy boundary $v_{mut}(t_{OS(s2mut)})$ is also crossed then we will stop the study for superior efficacy, and no more testing will be done for either PFS or OS.
 - If $u_{mut}(t_{PFS(s2mut)})$ is crossed but $v_{mut}(t_{OS(s2mut)})$ is not crossed then we will stop testing for PFS, however OS will be tested as planned at $s4mut$ (Step 4).
 - If $u_{mut}(t_{PFS(s2mut)})$ is not crossed then OS will not be tested during the second interim analysis; and go to step 3.
3. During the final PFS analysis, test PFS at $\alpha=0.0199$:
 - If the PFS efficacy boundary $u_{mut}(t_{PFS(s3mut)})$ is crossed then test OS at $\delta_{mut}(t_{OS(s3mut)})$.
 - If the OS efficacy boundary $v_{mut}(t_{OS(s3mut)})$ is also crossed then no more testing for either PFS or OS.
 - If $u_{mut}(t_{PFS(s3mut)})$ is crossed but $v_{mut}(t_{OS(s3mut)})$ is not crossed then we will continue test OS as planned (go to step 4).
 - If $u_{mut}(t_{OS(s3mut)})$ is not crossed then OS will not be tested; and no more testing on either PFS or OS.

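### The final PFS boundary is printed as two different thresholds, an input to the second futility criterion is mislabelled, and one stopping-probability cell contradicts its own table; the futility cut-off of 1.489 itself is right.

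*Protocol*

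**What the plan says.** The sample size statement (Protocol 10.8, SAP 3.14) is that "a total of 243 PFS events are required to have 83.80% power at an one-sided overall 2.0% level of significance", for a true hazard ratio of 0.6 and 1:1 allocation. The PFS looks are at 97, 185 and 243 events.

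- **Final boundary.** Protocol 10.7.1 and SAP 3.12.1 state that "the p-value that will be used to declare statistical significance at the final analysis will be 0.0199", with Z=2.054 in brackets. SAP 4.5.4 step 3 tests at 0.0199 and prints no Z value. SAP 4.5.3 sets the final boundary so that the cumulative one-sided alpha equals 0.02.
- **Futility.** At 97 events the cohort may stop if either of two criteria is met. Criterion 1 is a nominal p-value above 0.128 (Z=1.134), from the beta-spending function. Criterion 2 is a conditional probability below 0.20 that the final hazard ratio will be 0.6 or lower. Its cut-off is given as |Z|=1.489, p=0.068 and, in the SAP, hazard ratio 0.739. The formula is in Protocol 14.6.1 and SAP 4.6, where the critical value z_α' is described only as "Final boundary on Z scale", without a number.
- **Recalculation.** If event counts differ from plan, efficacy and futility boundaries are to be recomputed, and "the observed p-values at the interim analyses will be compared with the updated boundaries".
- **Stopping probabilities.** Under HR 0.6, Protocol Table 10-1 and SAP Table 3-10 give 0.34% for stopping for efficacy at interim 1. The Protocol note beneath says "The study will not stop for outstanding efficacy at the first (futility) interim analysis". SAP 4.5.4 step 1 begins "During the first PFS interim analysis, test PFS at" an alpha level for that look, and then has only a futility branch.

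**The concern.** These figures are decision thresholds for the primary endpoint. A p-value and a Z value printed as equivalents should lead to the same decision, and here they differ for a final Z between 2.054 and 2.056.

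The formula raises a different problem. An independent statistician who puts in the only final Z boundary that the plan contains cannot obtain the stated cut-off. The label and the alpha subscript both point to the efficacy boundary. If criterion 2 were recomputed that way at an observed event count, it would almost never trigger, and the stated stopping probabilities and power would no longer describe the design.

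The 0.34% cell leaves the reader unsure whether an efficacy stop was simulated at interim 1.

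**Working it through.** **Inputs.** One-sided alpha 0.02, D=243 events and HR 0.6 (Protocol 10.8); 1:1 allocation, so a=(1+1)²/1=4; interim 2 boundary p=0.0001, Z=3.719 at 185 events (Protocol 10.7.1); t=0.4 (Protocol 14.6.1).

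**1. Final boundary**

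- 1-Φ(2.054)=0.01999, which is 0.0200 to four decimals.
- Φ⁻¹(1-0.0199)=2.0558.
- Exact boundary: solve 0.0001 + P(Z₂<3.719, Z_F≥u)=0.02 with correlation √(185/243). This gives u=2.0538, nominal p=0.0200.
- Total alpha is 0.01999 when testing at Z=2.054 and 0.01990 when testing at p=0.0199. Both are within 0.02.

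Z=2.054 is therefore right to three decimals, and 0.0199 is the value that does not match it. The figure 0.0199 equals 0.02-0.0001.

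**2. Criterion 2 cut-off**

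Setting the printed formula equal to 0.20 and solving for the interim statistic gives

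z_t = [Φ⁻¹(0.20)·√(1-t) + z_α' - (-log 0.6)(1-t)·√(D/4)] / √t.

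The fixed terms are Φ⁻¹(0.20)·√0.6=-0.652, 0.5108×0.6×7.794=2.389 and √0.4=0.632.

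To reproduce the plan's figure, take z_α' as the Z value of a final hazard ratio of 0.6 at 243 events, 0.5108×7.794=3.981:

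- z_t=(-0.652+3.981-2.389)/0.632=1.487, p=0.0685, interim HR 0.740. The plan states 1.489, 0.068 and 0.739.
- Stopping probabilities at 1.489 with 97 events: Φ(1.489)=93.2% under HR 1 and Φ(1.489-2.516)=15.2% under HR 0.6. The plan states 92.98% and 15.31%.
- Simulated power with this rule is 84.0%, against the stated 83.80% and 83.95%.

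With z_α'=2.054, the only final boundary printed:

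- z_t=(-0.652+2.054-2.389)/0.632=-1.56, p=0.94, interim HR 1.37.

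**3. Effect of recalculating with the printed label**

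Because either criterion is enough to stop, criterion 1 at Z=1.134 would remain. Simulated Z-paths at 97, 185 and 243 events, with efficacy boundaries 3.719 and 2.054 and futility treated as followed, give:

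| Effective futility rule | Stop, HR 1 | Stop, HR 0.6 | Power, HR 0.6 |
|---|---|---|---|
| Z≤1.489 (criterion 2 as intended) | 93.2% | 15.2% | 84.0% |
| Z≤1.134 (criterion 1 only) | 87.2% | 8.4% | 90.4% |

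The plan's own figures for criterion 1 alone (Protocol Table 14-11, SAP Table 4-1) are 86.95% and 8.89%, in line with the second row.

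**4. Table 10-1 / SAP Table 3-10, HR 0.6**

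- The three increments sum to 0.34+38.50+45.45=84.29, but the cumulative figure is 83.95=38.50+45.45.
- Interim 2 shows 38.50 as both cumulative and incremental, which cannot be if 0.34 had already been spent.
- If the interim 2 threshold were applied at 97 events, P(Z₁≥3.719) under HR 0.6 would be 11.4%. The 0.34 does not come from that rule either.

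**The case against.** The strongest reply is that no threshold is wrong in substance. The cut-off 1.489 follows from criterion 2 as worded, because the event is a final hazard ratio of 0.6 or lower and the matching boundary is the Z value of 0.6. Anyone who obtained -1.56, an interim hazard ratio of 1.37, would see at once that it conflicts with the printed p=0.068 and HR 0.739. The recalculation sentence names the Haybittle-Peto boundary and the beta-spending function but not the conditional-probability criterion, so a literal recalculation of criterion 2 may never have been intended. The p/Z mismatch is 0.0001 and errs on the safe side. The 0.34 is not carried into the cumulative column. Protocol Amendment 5 records that the primary endpoint was met, so these looks lie in the past.

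All of this stands, and it sets the severity. It does not remove the defects, because the printed definition still fails to yield the printed cut-off and the table still contradicts its note.

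Three stronger readings are tempting, and the documents support none of them:

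- A reader might infer that 1.489 is itself an error. It is reproduced above from the stated criterion.
- A reader might infer that the mislabelled input would remove the futility rule altogether, leaving about 5.9% stopping under HR 1 and 97.3% power. Those figures require criterion 1 to be dropped, and the plan keeps it.
- A reader might infer that SAP 4.5.4 step 1 contains an efficacy stop. It names an alpha level but provides no efficacy action, and Protocol 10.7.1 and SAP 3.12.1 both rule out declaring superiority at that look.

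**Conclusion.** The concern holds as a documentation error of minor severity in three places.

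- The final boundary is printed as two thresholds that differ by about 0.0001 in p, or 0.002 in Z. Type I error is controlled under both.
- The label on z_α' does not produce the stated cut-off, which is correct and needs no change. If criterion 2 were recalculated with that label, stopping would fall to about 87% under HR 1 and 8% under HR 0.6, and power would be about 90% instead of 83.8%.
- The 0.34% cell cannot be reconciled with the table's note or its cumulative column.

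The figures assume proportional hazards, the usual normal approximation with information equal to events/4, looks at exactly 97, 185 and 243 events, and non-binding futility rules that are in fact followed. The size given for the mislabelled input also assumes that someone recalculates criterion 2 from the printed formula, which the text invites but does not explicitly require. Nothing here shows that any decision taken in the trial was wrong.

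**What to change.** 1. Print one matching pair for the final PFS boundary in Protocol 10.7.1, SAP 3.12.1 and SAP 4.5.4: either p=0.0200 with Z=2.054, or p=0.0199 with Z=2.056.
2. In Protocol 14.6.1 and SAP 4.6, define z_α' as the Z value of a final hazard ratio of 0.6, -log(0.6)·√(D/a)=3.98 at 243 events, and say that it is not the significance boundary. Leave 1.489, p=0.068 and HR 0.739 unchanged.
3. Set the interim 1 efficacy cells under HR 0.6 to 0 in Protocol Table 10-1 and SAP Table 3-10. The increments then sum to 83.95.
4. Reword SAP 4.5.4 step 1 as a futility assessment only, without an alpha level for PFS.

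The cost is a few words and numbers. The design, sample size, alpha allocation and futility cut-offs do not change.
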